4. SUBJECT SELECTION AND WITHDRAWAL CRITERIA

4.1. Number of Subjects

Subjects who meet all the following inclusion/exclusion criteria will be eligible for randomization into the study. The original plan was for approximately 583 subjects to be screened (with 532 randomized) to obtain 478 evaluable subjects (assuming 10% screen failure and 10% drop out rates). All evaluable subjects were obtained, and as the significance level was met at the interim efficacy of analysis, further enrollment will be stopped.

4.2. Inclusion Criteria

Subjects eligible for enrollment in the study must meet all of the following criteria:

1. Adults with documented diagnosis of CLL based on the modified IWCLL updated NCI-WG guidelines [Hallek, 2008]
2. At least PR according to the revised 2008 NCI-WG CLL criteria within 3 months of the response assessment after the last dose of 2nd/3rd line treatment
3. The anti-leukemic treatment before study entry should have been for at least 3 months or 3 cycles
4. ECOG Performance Status of 0-2
5. Signed written informed consent prior to performing any study-specific procedures

French subjects: In France, a subject will be eligible for inclusion in this study only if either affiliated to or a beneficiary of a social security category.

4.3. Exclusion Criteria

Subjects meeting any of the following criteria must not be enrolled in the study:

1. Known primary or secondary fludarabine-refractory subjects, defined as treatment failure (failure to achieve a CR or PR) or disease progression within 6 months [Hallek, 2008]
2. Prior maintenance therapy
3. Known transformation of CLL (e.g. Richter's transformation), prolymphocytic leukemia (PLL), or CNS involvement of CLL

4. Active Autoimmune Hemolytic Anemia (AIHA) requiring treatment except if in the opinion of the investigator it is thought not to affect the subject's safety, the conduct of the study or the interpretation of the data
5. Previous autologous or allogeneic stem cell transplantation
6. Chronic or current active infectious disease requiring systemic antibiotics, antifungal, or antiviral treatment such as, but not limited to, chronic renal infection, chronic chest infection with bronchiectasis, tuberculosis and active Hepatitis B or C
(Positive serology for Hepatitis B (HB) defined as a positive test for HBsAg. In addition, if negative for HBsAg but HBcAb positive (regardless of HBsAb status), a HBV DNA test will be performed and if positive the subject will be excluded*.)
7. Other past or current malignancy (with the exception of basal cell carcinoma of the skin or in situ carcinoma of the cervix or breast) unless the tumor was successfully treated with curative intent at least 2 years prior to trial entry except if in the opinion of the investigator it is thought not to affect the subject's safety, the conduct of the study or the interpretation of the data
8. Clinically significant cardiac disease including unstable angina, acute myocardial infarction within 6 months prior to screening, congestive heart failure, and arrhythmia requiring therapy, with the exception of extra systoles or minor conduction abnormalities except if in the opinion of the investigator it is thought not to affect the subject's safety, the conduct of the study or the interpretation of the data
9. History of significant cerebrovascular disease or event with symptoms or sequelae
10. Significant concurrent, uncontrolled medical condition that in the opinion of the investigator contraindicates participation in this study
11. Other anti-leukemic use of medications including glucocorticoids
12. Known HIV positive
13. Screening laboratory values:
 - Platelets < 50 x 10⁹/L
 - Neutrophils < 1.0 x 10⁹/L
 - Creatinine > 1.5 times upper normal limit (unless normal creatinine clearance)
 - Total bilirubin > 1.5 times upper normal limit (unless due to liver involvement of CLL or Gilbert's syndrome)
 - Alanine Aminotransferase (ALT) > 2.5 times upper normal limit (unless due to liver involvement of CLL)
 - Alkaline phosphatase > 2.5 times upper normal limit
14. Known or suspected hypersensitivity to ofatumumab that in the opinion of the investigator or medical lead contraindicates study participation

15. Subjects who have received treatment with any non-marketed drug substance or experimental therapy within 5-terminal half-lives or 4 weeks whichever is longer prior to first dose of study medication or currently participating in any other interventional clinical study

Note: Participation in any other interventional clinical study after disease progression during post PD follow-up is permitted

16. Lactating women, women with a positive pregnancy test at Visit 1 or women (of childbearing potential) as well as men with partners of childbearing potential, who are not willing to use adequate contraception from study start through one year following last ofatumumab dose. Adequate contraception is defined as abstinence, oral hormonal birth control, implants of levonorgestrel, estrogenic vaginal ring, percutaneous contraceptive patches, intrauterine device, and male partner sterilization if male partner is sole partner for that subject. For females in the USA, the use of a double barrier method is also considered adequate (condom or occlusive cap plus spermicidal agent).

* If HBV DNA is negative, subject may be included but must undergo HBV DNA monitoring (see Section 6.3.4). Prophylactic antiviral therapy may be initiated at the discretion of the investigator. Consult with a physician experienced in the care and management of subjects with hepatitis B to manage/treat subjects who are anti-HBc positive.

4.4. Withdrawal Criteria

Subjects may be withdrawn from investigational product at any time if it is the wish of the subject (or their legally acceptable representative) for any reason, the investigator judges it necessary due to medical reasons including disease progression or the subject becomes pregnant. (See also Section 8.3.5.) The subject will be evaluated for disease status and survival per the follow-up visit schedule outlined in Section 3.1.4.

Furthermore, a subject may withdraw from study participation (i.e., withdraw consent) at any time for any reason. The reason for withdrawal from study participation must be documented in the eCRF.

The investigator must make every effort to perform and document the following in the eCRF:

- Disease assessment
- Hematology and Chemistry
- Physical examination, vital signs and body weight assessment
- Response Assessment
- AE/SAE Assessment
- Concomitant Medication assessment
- Subject completion of PRO measures (EORTC QLQ-C30, EORTC QLQ-CLL16, EQ-5D and the Health Change Questionnaire)

For data collection purposes, subjects are considered as completing the study if they have died during the treatment or follow-up phases, are lost to follow-up, or withdraw consent.

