3.1.3. Treatment Phase

Subjects randomized to treatment arm A will receive ofatumumab whereas subjects randomized to treatment arm B will receive no further treatment (i.e. observation only).

Arm A:

Ofatumumab:

- 300mg IV Week 1 followed by 1000mg IV on Week 2
- 1000mg IV (1 dose every 8 weeks for up to 2 years following the first 1000 mg dose)

OR

Arm B:

- No further treatment (observation and assessments as per arm A)

Disease status assessments to determine subject response or progression will be performed approximately every 8 weeks for up to 2 years for both arms according to NCI Criteria [Hallek, 2008] and will include:

- Physical examination including lymph node examination, spleen and liver measurement, and detection of constitutional symptoms
- Peripheral blood sample evaluation of complete blood count (CBC) and differential (expressed in % and absolutes)

Monitoring and treatment of potential Tumor Lysis Syndrome (TLS) during the first cycle will be performed as per oncology standard of care.

Patient Reported Outcome (PRO) measures (EORTC QLQ-C30, EORTC QLQ-CLL16, EQ-5D) will be administered for completion by subjects at baseline, at each treatment visit beginning with Visit 3, at last visit, and at follow-up visits. A Health Change Questionnaire will be administered for completion by the subjects at all post baseline visits, as per Section 6.5.6.

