3.1.4. Follow-up Phase

Survival and disease status assessments (physical examination and evaluation of peripheral blood samples) will be performed post treatment every 3 months for 5 years after last treatment.

A bone marrow examination is required to confirm Complete Remission (CR) at least 2 months after completion of therapy and when a subject fulfills the International Workshop for Chronic Lymphocytic Leukemia (IWCLL) updated National Cancer Institute-Sponsored Working Group (NCI-WG) requirements for Complete Remission (CR) [Hallek, 2008]. Previous results may be used or if not available, a bone marrow exam may be done at screening. If a subject's response improves to a CR while on study, then a bone marrow examination is required to confirm CR at least 2 months after response as per the updated IWCLL NCI-WG requirements for CR [Hallek, 2008].

Additionally, CT Scans are required yearly while on study, including during follow-up, and at disease progression, whenever that may occur.

Subjects demonstrating disease progression will be followed for survival status until study completion. Follow-up assessment after disease progression on treatment will assess survival status, date of next CLL therapy, type of therapy and response to therapy. It is acceptable for the information for survival follow-up visits to be collected remotely (via telephone, email), as necessary. The frequency of the survival follow-up visits should be per local standard of care, suggested every 3 months for CLL. Minimally, this should be collected at least annually.

PRO measures (EORTC QLQ-C30, EORTC QLQ-CLL16, EQ-5D and a Health Change Questionnaire) will be administered for completion by the subject at follow-up visits, as per Section 6.5.6.

Please refer to Section 6: Study Assessments and Procedures for detailed assessment instructions.

Supplementary study conduct information not mandated to be present in this protocol is provided in the accompanying Study Procedures Manual (SPM). The SPM will provide the site personnel with additional administrative and detailed technical information.

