PML is a viral-induced demyelinating disease of the central nervous system usually occurring in the immunocompromised individual and has been reported with ofatumumab. JC virus (JCV) infection resulting in PML and death has been reported in rituximab-treated subjects with hematologic malignancies or with systemic lupus erythematosus, an indication for which rituximab has not been approved. Investigators and nurses should pay careful attention for signs and symptoms consistent with a diagnosis of PML. Signs and symptoms of PML include visual disturbances, ocular movements, ataxia, and changes in mental status such as disorientation or confusion. These symptoms are not an exhaustive list, and the investigator should exercise judgment in deciding to report signs and symptoms to sponsor promptly.

If a subject develops neurological signs or symptoms consistent with PML, treatment should be halted and the subject referred to a neurologist for evaluation. At a minimum, blood JCV PCR and/or MRI should be performed; if either test is positive, Cerebrospinal Fluid (CSF) JCV PCR should be performed. If blood JCV PCR and MRI are negative, the investigator should contact the Sponsor for appropriate action to be taken. If blood JCV PCR and/or MRI are positive, the subject should be withdrawn from treatment, proceed to the Follow-Up Period, and be followed until resolution. There are no known tests that can reliably determine who is at increased risk for developing PML. There are no known interventions that can reliably prevent PML or adequately treat PML if it occurs.

The investigator will do the following when reporting a serious infection (including PML) or sign/symptom consistent with PML.

- Refer to Section 6.4.10 of this document for further information and detailed guidance for completing and transmitting these and other SAE reports for subjects who experience a serious infection, malignancy, death, or sign or symptom of PML.
- Provide key source documentation for the Sponsor to assist with the safety evaluation process.

Examples of key source documents include but are not limited to: hospitalization records, discharge summaries, laboratory evaluations, biopsy results, culture/sensitivity results, death certificates, and autopsy reports.

If the subject has not otherwise been withdrawn from the study, then the investigator should contact the Sponsor to discuss the appropriate course of action regarding study continuation.

Monitoring of Hepatitis in patients:

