6.6. Pharmacokinetics

Blood samples will be collected from subjects receiving ofatumumab predose and 0.5 h after the end of the infusion (EOI) at treatment on Month 1 Week1 (Day 1), Month 1 Week 2 (Day 8), Months 3, 7, 13, 19 and 25. In addition, predose samples will be collected prior to ofatumumab administration on Months 5 and 9. A pharmacokinetic sample (and a HAHA sample) should also be obtained at the last treatment visit if it does not occur at a scheduled sampling time (e.g., if treatment is discontinued early). Samples will also be collected at any time of day during clinic visits at 3 and 6 months post-last ofatumumab dose. Table 5 provides the pharmacokinetic sample collection schedule.

Predose samples may be collected at any time prior to dosing, and 0.5 h post-EOI samples may be collected within a \pm 15 minute window around the scheduled time. The actual date and time of each sample collection will be recorded in the eCRF.

Table 5 Ofatumumab pharmacokinetic sample collection schedule

Month	Week	Visit	Sampling time
1	1	1	Predose, 0.5 h post-EOI
1	2	2	Predose, 0.5 h post-EOI
3	9	3	Predose, 0.5 h post-EOI
5		4	Predose
7		5	Predose, 0.5 h post-EOI
9		6	Predose
13		8	Predose, 0.5 h post-EOI
19		11	Predose, 0.5 h post-EOI
25		14	Predose, 0.5 h post-EOI
28		15	3 months after last dose ^{1,2}
31		16	6 months after last dose ^{1,2}

1. Collect sample at any convenient time on study day.

2. Collect sample relative to last dose of ofatumumab regardless of when it occurs

Sample collection, processing, and shipping instructions are provided in the study procedures manual.

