### **9.2.12. Extended Loss to Follow-up or Extended Time without an Adequate Assessment**

Since PFS is interval censored, extended loss to follow-up prior to PD or death increases the uncertainty when the event actually occurs. As such, PFS will be analyzed censoring for extended loss to follow-up to account for missed disease assessments prior to disease progression or death.

If 2.5 or more scheduled disease assessments are missed and are then followed by an assessment of PD or death, PFS will be censored at the last adequate assessment prior to PD or death. An adequate assessment is defined as an assessment where the investigator determined response and components of lab and clinical parameters (blood, lymph nodes, organ and constitutional symptoms) are available. The blood laboratory tests in the definition of the “adequate assessment” are haemoglobin, platelets, ANC and lymphocytes.

If the PFS event occurred after the 1st visit up to 2 years (on-treatment or on-study period) where scheduled disease assessments are planned every 8 weeks, a 2.5 assessment window of 140 days (8 weeks + 8 weeks + 4 weeks window) will be used to determine whether there was an extended time without adequate assessment. That is, if the time

difference between PD/death and last adequate assessment is more than 140 days, then PFS will be censored at the last adequate assessment prior to PD/death.

If the PFS event occurred during the follow-up where visits are planned every 3 months for 5 years, then as 2.5 assessment window of 210 days (3 months + 3 months + 1.5 months = 7.5 months = 30 weeks) will be used to determine whether there was an extended time without adequate assessment. This is, if the time difference between PD/death and the last adequate assessment is more than 210 days, then PFS will be censored at the last adequate assessment prior to PD/death.

The following is further explanation regarding the definition of extended lost-to-follow-up:

- 2.5 Assessment windows from last adequate assessment (prior to PFS Event assessment) to PFS Event.
  - If PFS Event occurred during – On-Study planned visits –
    - Visits are planned every 8 weeks after the 1st visit up to 2 years.
    - Window = 8 weeks + 8 weeks + 4 weeks = 20 weeks = **140 Days**.
  - If PFS Event occurred during - During Follow-Up planned visits
    - Visits are planned every 3 months for 5 years.
    - Window = 3 months + 3 months + 1.5 months = 7.5 months = 30 weeks = **210 days**.

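### Stopping ofatumumab early moves a subject to 3-monthly disease assessments while observation stays 8-weekly for two years: a small one-sided delay in detecting progression, and an ambiguous censoring gap

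*Protocol*

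**What the plan says.** - **Treatment phase.** Protocol 3.1.3 has disease status assessed "approximately every 8 weeks for up to 2 years for both arms according to NCI Criteria". The observation arm is described as "No further treatment (observation and assessments as per arm A".
- **After stopping drug.** Protocol 4.4 covers subjects withdrawn from investigational product for any reason and then states: "The subject will be evaluated for disease status and survival per the follow-up visit schedule outlined in Section 3.1.4". Protocol 3.1.4 says these assessments "will be performed post treatment every 3 months for 5 years after last treatment".
- **Supporting text.** Under the pharmacokinetic schedule (Protocol 6.6, Table 5), the footnote to Visits 15 and 16 reads "Collect sample relative to last dose of ofatumumab regardless of when it occurs". Protocol 6.4.6, on positive tests for progressive multifocal leukoencephalopathy, says "the subject should be withdrawn from treatment, proceed to the Follow-Up Period, and be followed until resolution". Both treat follow-up as starting at the actual last dose.
- **Text pointing the other way.** SAP Section 3 describes 8-weekly assessment to two years and 3-monthly thereafter in both arms. Protocol Appendix 1 gives the follow-up visits fixed weeks, 109 to 337. Neither says what applies after an early stop.
- **Analysis.** Early stoppers who remain on study stay in the PFS analysis (Protocol 8.3.5, SAP 9.1), and progression takes the investigator's assessment date (SAP 11.1).
- **Censoring gap.** SAP 9.2.12 allows 140 days between the last adequate assessment and the event in the 8-weekly phase. "If the PFS event occurred during the follow-up where visits are planned every 3 months for 5 years", it allows 210 days, shortened to 168 and 196 days at the first two follow-up assessments.

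**The concern.** The primary endpoint is investigator-assessed PFS in an open-label trial, so both arms should be examined equally often whatever happens to drug. As written, only the ofatumumab arm has a product to withdraw from, so only its subjects can move to the sparser schedule inside the first two years. A progression in such a subject waits longer to be seen and receives a later date. The direction is fixed and favours ofatumumab.

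The same ambiguity reaches the censoring rule, because the gap depends on whether an event belongs to follow-up, and the SAP does not say when follow-up begins for someone who stopped early. The three PFS sensitivity analyses in SAP 11.1 vary the assessor and the use of CT. None varies visit timing.

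**Working it through.** **1. The plan's own figures.** Inputs from Protocol 8.2.1: medians 28 and 39.2 months (HR 28/39.2 = 0.714), 5% two-sided, 80% power, 1:1.
- Schoenfeld: 4 × (1.960 + 0.842)² / (ln 0.714)² = 31.40 / 0.1132, giving 278 events. Freedman gives 283. The plan states 280.
- Power at 280 events: Φ(0.3365 × √280 / 2 − 1.960) = Φ(0.855) = 0.80, as in Table 6.

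These figures are not in dispute.

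**2. Detection lag.** If progression falls evenly between visits, the mean wait to the next visit is half the interval. With the SAP 9.2.4 month of 30.4375 days, three months is 91.3 days.
- 8-weekly: 56 / 2 = 28.0 days.
- 3-monthly: 91.3 / 2 = 45.7 days.
- Difference: 17.7 days (2.5 weeks) on average. The longest possible waits differ by 91.3 − 56 = 35.3 days.

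**3. Effect on the hazard ratio.** Simulation with 400,000 subjects per arm, exponential PFS, visits jittered by ±7 days, and drug stopped uniformly over 96 weeks independently of progression. Progression is dated at the next scheduled visit. The same subjects are run with and without the switch to 3-monthly visits, and the factor is the ratio of the two Cox hazard ratios.

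| Medians, ofatumumab vs observation (months) | 10% stop early | 40% stop early | 100% stop early |
|---|---|---|---|
| Design: 39.2 vs 28 | 0.9992 | 0.9967 | 0.993 |
| Interim: 29.4 vs 15.2 | 0.9987 | 0.9944 | 0.9865 |
| No effect: 28 vs 28 | 0.9990 | 0.9963 | 0.9922 |
| No effect: 15.2 vs 15.2 | 0.9984 | 0.9936 | 0.9839 |

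Affected subjects are detected about 20 days later. This is slightly above 17.7 because the last 3-monthly interval can run past the end of the 8-weekly phase. With 40% stopping at the interim medians, 8.1% of the arm is affected, so the delay averaged over the whole arm is 0.081 × 19.6 = 1.6 days.

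**4. Consequences.**
- Interim estimate: 0.50 / 0.994 = 0.503.
- Type I error: a factor f shifts the log-rank statistic by |ln f| × √events / 2. For f = 0.995 at 280 events the shift is 0.042, and the two-sided rejection rate goes from 0.0498 to 0.0500. For f = 0.99 it is 0.0506. At 187 events and the 0.001 level, the rates are 0.00101 and 0.00103.
- Power at the design medians with f = 0.9967: Φ((0.3365 + 0.0033) × 8.367 − 1.960) = Φ(0.883) = 0.81, against 0.80.

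**5. The censoring gap under each reading,** for an early stopper and an observation subject at the same time since randomisation.
- Follow-up starts at the early stop: 168 to 210 days for the stopper, 140 for the observation subject. The tolerance differs in days.
- Follow-up starts after two years: 140 days for both. One missed visit leaves a gap of 2 × 91.3 = 183 days for the stopper, so the event is censored. It leaves 2 × 56 = 112 days for the observation subject, so the event counts. The tolerance differs in missed visits.

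**The case against.** The best case against is that 8-weekly assessment for two years in both arms was always intended. Protocol 3.1.3, SAP Section 3 and the fixed follow-up weeks in Appendix 1 all fit that. But 4.4 is the only instruction written for early stoppers, and a site following it would change the schedule. If the common calendar was intended, 4.4 contradicts it.

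Several counterpoints stand:
- The lag is an upper figure. Progression found between scheduled visits counts on its assessment date (SAP Table 1), and Protocol 6.3 allows extra haematology.
- The share stopping early is assumed.
- Table 2.3000 in the plan for the 280-event analysis (PFS with all events included) bears on the gap rule, though not on visit timing.
- Enrolment is closed, the PFS analysis will not be updated, and the remaining results are descriptive. A protocol sentence cannot alter visits already made.

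A reader might infer that the SAP definitely treats the arms differently: that progression in Month 12, 150 days after the last adequate assessment, is an event for a stopper and censored for an observation subject. The documents do not establish this. SAP 9.2.12 ties the 140-day gap to the period from the first visit to two years and names the on-study as well as the on-treatment period. Read by calendar, that event is censored in both arms.

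A reader might also think that imposing the calendar gap on existing data would repair matters. By step 5, it would censor a 3-monthly subject after one missed visit but not an 8-weekly one, removing ofatumumab events.

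**Conclusion.** The visit asymmetry follows from Protocol 3.1.3, 3.1.4 and 4.4 read together, and its direction favours ofatumumab. It concerns only subjects who stop drug without progression and then progress within two years. Their detection is later by up to about 18 to 20 days on average. The factor on the Cox hazard ratio is about 0.999 to 0.994 for 10-40% early stopping. This assumes exponential PFS, stopping unrelated to progression, and detection only at scheduled visits.

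The effect cannot account for the interim hazard ratio of 0.50 and leaves alpha and power essentially as planned, so it gives no ground for doubting the PFS result. The censoring gap for early stoppers is ambiguous, and uneven under either reading while visit intervals differ. Severity is minor: an inexpensive improvement.

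**What to change.** **In the plan.** Reconcile Protocol 3.1.3, 3.1.4 and 4.4 with SAP Sections 3 and 9.2.12. PFS disease-status assessments (physical examination and blood count) should follow one calendar from randomisation in both arms: 8-weekly to about two years, then 3-monthly, whether or not ofatumumab continues. The 140- or 210-day gap should follow that same calendar.

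**Cost.** A sentence or so in each document. Early stoppers attend about 52/8 − 4 = 2.5 more visits per year, using examinations already in the schedule.

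**For data already collected.** Do not change the gap rule on its own. Tabulate assessment intervals by arm, report PFS under both readings of the gap rule alongside Table 2.3000, and add an interval-censored PFS sensitivity analysis. This needs no new data.
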